- vii) Lives within 2 hours driving distance from Toronto up to London, Ontario OR willing to travel to either HB or TVCC for first in-person coaching session if randomized into coaching group

Child exclusion criteria:

- i) Surgery in past 6 months or upcoming 12 months that may impact PA or dietary intake (e.g. orthopedic surgery or neurosurgery)
- ii) Medical condition severely restricting diet
- iii) Underweight (less than fifth percentile)
- iv) Receiving specialist dietetic services

Parent inclusion criteria:

- i) Primary caregiver to a study participant
- viii) Can communicate in English and respond to questions requiring some reflection and insight

Sample size

Feasibility studies do not assess intervention efficacy and therefore do not require formal sample size calculations [33, 85]. The sample size ($n=30$) was set as a minimum needed to assess the key feasibility issues, as per feasibility best practices [86]. Fifteen SFC-Peds participants will suffice to show

Children and Teens in Charge of their Health: A feasibility study of solution-focused coaching to foster healthy lifestyles in children and young people with physical disabilities.

a tendency ($p < 0.10$) within the intervention group of behavioural change assessed by Goal Attainment Scaling (GAS; see ‘Outcomes’), equal to an effect size of 0.55 with a power of 0.80. The responsiveness of the secondary outcome measures will be compared with goal scores for evidence of concordance, e.g. a tendency of correlation between behavioural change and the Arc’s Self-Determination Scale. *Post hoc* estimates of variance will be key for the full trial’s design as they will inform the power calculations of the eventual RCT [85]. The sample size will allow us to assess recruitment success and show whether testing procedures, coaching goals and follow-up sessions are consistent across groups, mobility levels and sites. This sample size will also provide sufficient data for the qualitative work we are proposing to explore acceptability [87, 88].

Recruitment

We will recruit 15 children with SB and 15 children with CP (a total of 30 participants) and their parents from Holland Bloorview and TVCC.

Recruitment at Holland Bloorview

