At this session, the RC will clarify any concerns, and answer any questions clients or parents might have and will judge the child's capacity to provide informed consent, guided by a structured tool (see Appendix 3). If the RC judges the child to have answered questions about the study with reasonable understanding, the child will sign the Informed Consent Form (ICF) (see Appendix 4). Otherwise, a parent will sign the ICF and the child will provide their assent (see Appendix 5). For parents who are willing to participate in the interviews and parent measures the parent will sign the ICF for their own participation in the study. The RC obtaining informed assent from prospective participants (children) will familiarize the potential participant about assent by explaining what free, informed consent is and how research is different from clinical care. The RC will have an open and age appropriate discussion with each child to assess readiness for assent. The RC may consult the parent to identify accommodations to assist in decisions to participate. The assent and consent forms will be provided prior to this discussion in order for families to review them on their own. While meeting with the client and parent, the RC will clarify any concerns, and answer any questions clients or parents might have. During this process, the highly experienced RC will observe and listen for any verbal and nonverbal indications of dissent. Furthermore, the RC will ensure ongoing informed assent by reconfirming agreement to participate throughout the study. At the end of the study, the family will receive a study summary letter at the end of the study. The local REB fully endorses these processes.

Randomization

Once participants have provided written informed consent and completed all baseline measures, they will be randomized into the study. The PLAN procedure of SAS/STAT software will create a random sequence to test randomization. Randomization block size will not be known to research staff to ensure blinding. Group allocation occurs after baseline assessment, stratified by diagnosis and recruitment site.

Children and Teens in Charge of their Health: A feasibility study of solution-focused coaching to foster healthy lifestyles in children and young people with physical disabilities.

Standard care

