Time 4 (SFC-Peds group): Children and their parents in the SFC-Peds group will undertake separate in-depth interviews facilitated by a qualitative interviewer to explore their experiences after coaching completion, perceived impact of intervention, barriers/facilitators to maintaining PA and dietary habits, and any unmet needs (see Appendix 16 for interview guide). Children will be asked to select 6-8 of their photographs taken since Time 2 to share with the interviewer. This will help remind children of their lifestyles in the previous six months, and enable them to speak in more depth about their feelings and experiences [106]. Each child will first be asked to explain why he/she took the photo, its meaning, what it shows of his/her coaching experience and the time since it ended.

Survey Time 4 (Control group only)

Time 4 (Control group): Children in the control group ($n=15$) will complete a Time 4 survey (see Appendix 17) regarding what they liked most/least about the study, any changes in health habits in the previous 12 months, acceptability of not getting the intervention, and tolerance of assessment protocols [30].

Qualitative Interview (Coaches only)

Time 4 (Coaches): Coaches will be interviewed to explore their experiences of delivering the intervention, e.g. challenges/facilitators, optimal coaching doses, use of technology (see Appendix 18).

Children and Teens in Charge of their Health: A feasibility study of solution-focused coaching to foster healthy lifestyles in children and young people with physical disabilities.

SECONDARY OBJECTIVE: *To determine the responsiveness of outcome measures to SFC-Peds coaching over 12 months.*

The following measures (excluding gender and date of birth) will be administered at Times 1, 2, 3, and 4 for all participants (approximately 1.5 hours duration). Issue identification and goal attainment measures are administered to SFC-Peds participants only with the first assessment conducted during the first coaching session. Measures have been selected based upon evidence of their responsiveness to change and psychometric properties in previous health promotion interventions [18]. Parent and child report questionnaires may be completed at home or online if the family prefers.

Participant characteristics

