DEMOGRAPHICS: Gender, date of birth, ethnicity, diagnoses, medications, current sports involvement (see Appendix 19 for demographics form). Questions from the International Study of Childhood Obesity, Lifestyle and the Environment survey (see Appendix 20) about the child's environment (e.g. accessibility of play areas) will also be collected [107].

FUNCTIONAL MOBILITY: The six-minute walk test for walkers [108] and the six-minute push test for non-walkers [109] (see Appendix 21).

Primary outcome measure

ISSUE IDENTIFICATION AND GOAL ATTAINMENT (CHILD REPORT):

Within-group change will be assessed using the Canadian Occupational Performance Measure (COPM) (see Appendix 22), which identifies the person-centred goal performance issues to improve, and assesses changes in occupational performance and satisfaction. Participant goal attainment will be assessed using Goal Attainment Scaling (GAS) (see Appendix 23), by defining five levels of goal attainment, thus ensuring that all attainment levels are mutually exclusive and measurable. This is an

Children and Teens in Charge of their Health: A feasibility study of solution-focused coaching to foster healthy lifestyles in children and young people with physical disabilities.

objective measure of behaviour change [110]. To minimize bias, GAS and COPM re-assessment will be conducted by a coach who has not worked with the child.

Secondary outcomes measures:

Between group change will be examined using the following measures:

BEHAVIOURAL ASSESSMENTS (CHILD REPORT):

Physical activity: The Habitual Activity Estimation Scale [111] (see Appendix 24) estimates time spent inactive, somewhat inactive, somewhat active, and very active, and shows good correlation with moderate to vigorous PA measured by accelerometry in our population ($p=0.02$) [112, 113].

Diet: The Dietary Screener Questionnaire (see Appendix 25) assesses dietary intake over the past 30 days and is validated against 24 hour multiple recall [114].

PSYCHOSOCIAL ASSESSMENTS (CHILD REPORT):

Self-determination: The *Arc's Self-Determination Scale* (see Appendix 26) has excellent reliability/validity with children with disabilities [64] and will assess self-determination to provide insight into potential mechanisms of behaviour change.

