Self-efficacy: The *PA Self-efficacy Scale* (see Appendix 27) assesses confidence in the ability to be physically active when faced with challenges [115], with good internal consistency ($\alpha=.54-.71$) and test-retest reliability (ICC= .61-.82). High self-efficacy scores are significantly associated with greater moderate-vigorous physical activity [116]. *Self-efficacy for healthy eating* (see Appendix 28) assesses participants' feelings of competence for making healthy food choices in: social, emotional, and typical situations [117]. Higher scores are associated with healthy food intake ($\beta = .33, p < .01$), test-retest reliability (ICC= .80) [118].

BODY COMPOSITION (CHILD ASSESSMENT):

Children and Teens in Charge of their Health: A feasibility study of solution-focused coaching to foster healthy lifestyles in children and young people with physical disabilities.

Weight, height/length, waist circumference, and skinfold thickness (see Appendix 29 for record form) will be assessed, using standard guidelines [119].

Weight: Participants will be weighed minimally clothed (e.g. t-shirt, light shorts) without shoes to the nearest 100 grams using a chair scale.

Height: Those able to stand will be measured to the closest millimeter with a portable stadiometer or length measuring board. For those with severe contractures, careful segmental measurement will be conducted of the child's length in supine. Arm span and ulna length will also be measured as they offer useful proxies for length in children with lower extremity deformities [127, 128].

Body Mass Index (BMI): BMI will be calculated using both height and length as kilograms per meter squared (kg/m^2) and classified using Centres for Disease Control and Prevention cut-offs (85th–95th centile=overweight, above 95th percentile=obese) [120].

Waist circumference: Waist circumference (WC) has been shown to correlate well with fat mass as measured by dual-energy X-ray absorptiometry (DXA) [129-132] and has been specifically recommended for assessing body fat of children with SB [133] WC will be measured using a flexible tape measure at the narrowest level between the lower costal border and the iliac crest, over light clothing. Children with WC \geq 90th percentile have shown to be at higher risk of cardiovascular indicators [134, 135]. The RA will confirm lesion level using medical records and note any bulky masses, liposuction incision marks or spinal curvature.

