Skinfold thickness: Skinfold thickness (SFT) is strongly associated with cardiovascular risk factors in children [136]. Tricep and subscapular skinfold thickness will be assessed, as per best practice [137] using Lange callipers (Cambridge Scientific Industries). Subscapular SFT in particular has

Children and Teens in Charge of their Health: A feasibility study of solution-focused coaching to foster healthy lifestyles in children and young people with physical disabilities.

previously demonstrated excellent test-retest reliability when conducted by skilled practitioners [127, 133]. The Slaughter equation will be used to assess body fat [138].

HOME AND ENVIRONMENT ASSESSMENT (PARENT REPORT):

The Family Eating and Activity Habits Questionnaire (see Appendix 30) is a 32-item parent-report assessment to assess the health behaviours of family members as well as the nature of the home environment [121]. It has high internal consistency (0.76-0.87) and test-retest reliability (0.75-0.89). These data will provide context for the children's behavioural outcomes, and allow us to examine the impact of the coaching on the family over time, which will also be examined in qualitative interviews with parents and children.

Post-Study

Following completion of the study, both child and their parent will be thanked and provided with a \$20 gift card for each visit (\$25 for the final visit) as a token of appreciation. Participants will also be offered volunteer hours. Families will be reimbursed for their parking expenses. Additionally, all participants who have completed all of the assessments will be entered into a prize draw for a gift card of \$150 at the end of the study. Participants and their parents will be asked if they wish to receive a summary of the research once the study is completed.

DATA ANALYSES

Sample characteristics will be summarized using descriptive statistics. Inferential statistics are not used in feasibility studies [82].

PRIMARY OBJECTIVE: Feasibility will be assessed using descriptive statistics using our *a priori success criteria* [82]. We will explore any sample/group differences between completers (complete Time 1 and Time 4 measures) and non-completers. We will also determine if there are sample and

Children and Teens in Charge of their Health: A feasibility study of solution-focused coaching to foster healthy lifestyles in children and young people with physical disabilities.

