SECONDARY OBJECTIVE: Measure responsiveness will be established by pre-post intervention differences using effect sizes (Cohen's *d*) and confidence intervals both within and between groups. It is well accepted to examine mean score changes for clinically significant differences pre and post intervention without calculating statistical significance (e.g. a score change of at least 2 points on the COPM is considered clinically significant [38]). We will therefore be able to assess the potential value of SFC-Peds over receiving printed materials only by examining goal scores over time. Our secondary outcomes will be compared with objective behaviour change (goal attainment) for concordance (e.g. whether successful goal attainment corresponds with increased self-determination). We will examine differences in outcome measures by disability, functional mobility, gender and age.

CHALLENGES

Our intervention (SFC-Peds) is largely virtual to reduce burden and enhance adherence [43]. All participants will receive gift cards for completing assessments to reduce attrition; this is a key feasibility outcome, especially in the control group. To reduce possible biases, participants will not meet during the study and coaches will not be involved in standard care. Standardized training (by 3 certified coaches) will be provided. Assessors will be asked which group they think participants are in; blinding success is indicated by accuracies at or below chance level. If adaptations are needed for the RCT, 'A process for Decision making after Pilot and feasibility Trials' (ADePT) [124] will be followed.

KNOWLEDGE TRANSLATION (KT)

A KT planning template [40] will ensure our findings have maximum reach yet are appropriate for feasibility study outcomes. The plan capitalizes on close collaboration of knowledge users and researchers within our investigative team. Integrated KT is promoted throughout the project by the involvement of clinical, family and knowledge user stakeholders, to ensure that the outputs meet the needs of the end users [125]. Holland Bloorview Research Family Engagement Committee members

Children and Teens in Charge of their Health: A feasibility study of solution-focused coaching to foster healthy lifestyles in children and young people with physical disabilities.

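### Between-group change on the secondary measures is planned as a pre-post difference; ANCOVA on the Time 1 value would usually be slightly more precise at no data cost (low priority)

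*Combined protocol and SAP*

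**What the plan says.** The section on secondary outcome measures assigns physical activity, diet, self-determination, self-efficacy, body composition and family habits to a comparison of the arms: "Between group change will be examined using the following measures". Data Analyses, Secondary Objective, gives the method: "Measure responsiveness will be established by pre-post intervention differences using effect sizes" (Cohen's d), with "confidence intervals both within and between groups". No baseline-adjusted model is named, nor the SD that standardises d.

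The Time 1 values that adjustment would need are already collected. Under the secondary objective in Study Assessments, the measures "will be administered at Times 1, 2, 3, and 4 for all participants". The Randomization section confirms that Time 1 precedes allocation: "Group allocation occurs after baseline assessment, stratified by diagnosis and recruitment site".

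The opening of Data Analyses says "Inferential statistics are not used in feasibility studies", but the between-group intervals remain in the plan. The Sample size section says that post hoc "estimates of variance will be key for the full trial".

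Goal Attainment Scaling and the COPM are given to the coached arm only, so this point does not concern them.

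**The concern.** A difference in mean change subtracts the whole Time 1 value from the follow-up value. When the pre-post correlation is below 1 and the SDs are similar, that over-corrects: the best coefficient for Time 1 is the regression slope, which is then less than 1. ANCOVA estimates the slope and removes the excess noise, at the price of one degree of freedom and a slope estimated from few children. With 15 per arm that price is not negligible, so the question is whether a gain survives it.

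Little is at stake. The between-group intervals will be wide under either method, and none of the feasibility criteria uses them. The interest lies in a nearly free improvement in precision, and in leaving the full trial with variance figures that serve whichever analysis it adopts.

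**Working it through.** **The plan's own figure.** The only sample-size figure concerns within-group goal attainment: 15 children, p < 0.10, effect size 0.55, power 0.80. With a one-sided 0.10 level, n = ((1.282 + 0.842)/0.55)² = 14.9, so 15 is reproduced. The plan gives no figure for the between-group comparison.

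**Inputs.**
- Arms of 15 and 15 (Design), so N = 30.
- The attrition criteria are 85% completing Times 1 and 4 (0.85 × 30 = 25.5, about 26) and 75% completing all assessments (22.5, about 22).
- The pre-post correlation ρ is not in the documents and is assumed. The nearest guide is test-retest reliability: .61–.82 (physical activity self-efficacy), .80 (healthy-eating self-efficacy) and 0.75–0.89 (family questionnaire). Correlations over 6 to 12 months are likely to be lower.
- Equal SD σ at both times and a common slope are assumed.

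**Formulas.** Variance of the between-group difference:
- Change score: 2σ²(1 − ρ) × 4/N, with t on N − 2 df.
- ANCOVA on Time 1: σ²(1 − ρ²) × 4/N × (1 + 1/(N − 4)), with t on N − 3 df. The last factor is the average cost of chance baseline imbalance with an estimated slope.
- Variance ratio: (1 + ρ)/2 × (1 + 1/(N − 4)).

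**Example, ρ = 0.7, N = 30, σ = 1.**
- Change: 2 × 0.3 × 0.1333 = 0.0800; SE 0.283; half-width 2.048 × 0.283 = 0.579.
- ANCOVA: 0.51 × 0.1333 × 1.0385 = 0.0706; SE 0.266; half-width 2.052 × 0.266 = 0.545.
- Ratio 0.941, so the interval is 6% narrower.

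**Expected 95% interval width, ANCOVA divided by change score** (also allowing for the mean of the sample SD on each df):

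| ρ (assumed) | N = 30 | N = 26 | N = 22 |
|---|---|---|---|
| 0.3 | 0.823 | 0.826 | 0.831 |
| 0.5 | 0.884 | 0.887 | 0.892 |
| 0.61 | 0.916 | 0.919 | 0.924 |
| 0.7 | 0.941 | 0.944 | 0.950 |
| 0.8 | 0.968 | 0.972 | 0.977 |
| 0.89 | 0.992 | 0.996 | 1.001 |
| 0.95 | 1.008 | 1.011 | 1.017 |
| Break-even ρ | 0.92 | 0.91 | 0.88 |

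**Simulation** (stratified allocation, assumed 2:1 site split, assumed blocks of 2 or 4, true effect 0.5 SD, random dropout to 26). It agrees with the table. Mean half-widths in SD at N = 30, change against ANCOVA, are 0.740/0.655, 0.576/0.542 and 0.470/0.455 at ρ 0.5, 0.7 and 0.8. Coverage is about 95% for both, and the mean change-score estimate is 0.49 to 0.51.

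**In participants.** To match the ANCOVA interval from 30 at ρ 0.5, 0.7 and 0.8, the change score would need about 38, 34 and 32.

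**Strata.** Adding diagnosis and site costs about 1 point of width at N = 30 and 1 to 2 points at N = 26 when they are unrelated to outcome. If the diagnoses differ by 1 SD, it gains about 2 points (N = 30) or 1 point (N = 26) at ρ 0.5, and nothing material at 0.7 or 0.8.

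**Sizing the full trial.** Using a change-score variance for a trial analysed by ANCOVA oversizes it by 2/(1 + ρ) − 1, which is 33%, 18% and 11% at ρ 0.5, 0.7 and 0.8. For comparison, a variance on 28 df has a 95% interval of 0.63 to 1.83 times its estimate.

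**The case against.** The strongest reply is that no error has been shown. The planned estimator is valid, the stated objective is responsiveness rather than efficacy, and standardised pre-post change describes responsiveness directly. That stands for the within-group description, which should stay. It does not settle the between-group contrast, which the plan also intends to report with intervals; the remark about inferential statistics does not remove them.

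Second, the gain is assumed and not guaranteed. Over the reliability range quoted in the documents it runs from 8% at 0.61 to 1% at 0.89 with 30 participants, and it vanishes at 0.89 with 22. In a single trial of 30 the ANCOVA interval is the wider one in about 9%, 24% and 36% of runs at ρ 0.5, 0.7 and 0.8, and with 26 completers in 13%, 28% and 41%. This stands and is why the priority is low. The gain is on average, and costs nothing in data.

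Third, the widths above are for a raw mean difference, whereas the plan attaches its intervals to Cohen's d. If d uses the pooled Time 1 SD, the ratios barely move: 0.887, 0.943 and 0.969 at ρ 0.5, 0.7 and 0.8. If d uses the change SD, the scale itself depends on ρ: that SD is σ√(2(1 − ρ)), equal to σ only at ρ = 0.5 and 0.63σ at ρ = 0.8. This supports naming the SD.

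Fourth, the oversizing argument needs two things that the plan does not state: that only the change-score SD is reported, and that the full trial uses ANCOVA. That is right. The error would also be conservative and smaller than the sampling error of the variance, so the argument carries little weight.

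**Conclusion.** The concern holds as a low-priority improvement in efficiency, not as a fault in validity. For measures with a pre-post correlation of roughly 0.5 to 0.8, ANCOVA on Time 1 gives between-group intervals about 12% to 3% narrower on average with 30 participants, and about 11% to 3% narrower with 26. Near 0.9 the methods are equivalent, and above that ANCOVA is marginally worse: about 1% wider on average at 0.95, and wider in about two thirds of single trials. The body-composition measures ("Weight, height/length, waist circumference, and skinfold thickness") may well be in that group, although the documents give no figure. The sizes rest on assumed correlations, equal SDs at both times, a common slope and dropout at random. The unnamed SD for d is a smaller reporting gap that should be closed whichever estimator is kept.

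**What to change.** - Estimate the between-group difference on each secondary measure at Times 2, 3 and 4 by ANCOVA on the Time 1 value, with a 95% interval. Keep pre-post change for within-group responsiveness.
- Diagnosis and site may be added because allocation is stratified by them, but not in the expectation of greater precision.
- For very stable measures such as body size, the change score is equally acceptable if it is named in advance.
- State that d is standardised by the pooled Time 1 SD.
- Report the raw SDs, the residual SD and the pre-post correlation with its interval. The correlation will be imprecise: an observed 0.7 from 30 children has a 95% interval of about 0.45 to 0.85.

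The cost is a few lines of analysis text and code, with no new data. The price is one degree of freedom (three with diagnosis and site). With those two terms, the share of single trials in which the interval is wider than the change-score one rises to about 14%, 31% and 43% at ρ 0.5, 0.7 and 0.8 with 30 participants, and 21%, 38% and 49% with 26.
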